Adding acceptance and mindfulness-based treatment strategies with CM may lead to improved abstinence outcomes. While highly effective, CM response is variable with significant rates of non-response, even to high-magnitude rewards. Little is known about individual-level characteristics associated with CM response, with the exception of intake urine status considered a marker of disorder severity.^{15,18,19} To our knowledge, we reported the first study examining **modifiable** cognitive-affective characteristics associated with CM response.²⁰ Ninety-nine treatment-seeking patients with CUD received 4 weeks of high-magnitude CM-based treatment targeting abstinence initiation.¹² A post-hoc comparison of responders, i.e., those achieving two consecutive weeks of cocaine-negative urine screens, and non-responders was performed on pretreatment measures of negative affect, experiential avoidance, cocaine craving/withdrawal symptoms, and impulsivity. Notably, while the groups reported similar levels of negative affect, impulsivity, and craving/withdrawal, the non-responder subgroup had higher levels of experiential avoidance (EA). In other words, non-responders differed from responders in their approach to handling negative internal experiences (e.g., craving, negative emotions). EA, or the tendency to avoid or respond inflexibly with drug use behaviors when experiencing aversive states, is thought to provide negative reinforcement for continued use despite the availability of competing non-drug rewards. These findings suggest that targeting problems in EA and behavioral flexibility may prove to be effective in enhancing response to CM.

Acceptance and Commitment Therapy (ACT) is a third generation CBT intervention, emphasizing the role of EA and inflexibility as key mechanisms underlying and positively correlated with psychopathology including drug use.^{21,22} ACT uses experiential exercises and metaphors to change the function of distressing thoughts and feelings, essentially helping clients make decisions and choices based on personal goals and values rather than on avoidance or control through substance use.²³ By reducing EA and improving distress tolerance, ACT *may help facilitate sensitivity to, and contact with, non-drug sources of reward made available via CM.*

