1. To determine if ACT enhances response to a high-magnitude CM procedure targeting cocaine-negative urines. It is hypothesized that initial treatment (4 weeks) with ACT and CM (ACT+CM) will produce higher response (abstinence) rates than initial treatment that combines standard Drug Counseling with CM (DC+CM).
 - 1.a. To determine if pretreatment EA level moderates the effects of ACT+CM on initial response. It is hypothesized that the benefit of ACT+CM over DC+CM on initial response (abstinence) rates will be greater in the subgroup of individuals with higher pretreatment EA scores.
 - 1.b. To determine if the effects of ACT+CM are mediated by changes in EA and reward sensitivity. It is hypothesized that ACT+CM effects on initial treatment response will be mediated by the primary hypothesized treatment mechanisms, EA and reward sensitivity.

Secondary Aims/Hypotheses:

2. To determine the best sequencing of treatment for initial non-responders. For initial non-responders, it is hypothesized that continued ACT+CM treatment with pharmacotherapy (modafinil) augmentation will be most effective in promoting abstinence relative to treatment combinations involving DC and/or placebo.
3. To determine the best sequencing of treatment for initial responders. For initial responders, it is hypothesized that continued ACT+CM will be more effective (higher abstinence rates; < 46% relapse rate) than continued DC+CM.

Study Design

Overall Research Strategy. We propose an adaptive, two-stage SMART design to test the primary research hypothesis that ACT, when used in combination with CM, will increase initial treatment response rates. Secondary hypotheses will determine the probability of benefit associated with two sequences of treatments, specifically, continued ACT+CM for initial treatment responders (dashed lines in **Figure B.3.2.i**) and continued ACT+CM with modafinil augmentation for initial treatment non-responders (double lines in **Figure B.3.2.i**).

Overview of Study Design. Note: SR=stratified randomization; R=randomization; ACT=Acceptance and Commitment Therapy; DC=Drug Counseling; CM=Contingency Management; PLA=placebo; MOD=modafinil. Abstinent=6 consecutive (2 wks) cocaine-negative (BE<150 ng/ml) urines samples.

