Phase 1 treatments. Consenting subjects will be assigned to one of the two 4-week Phase 1 treatments, ACT+CM or DC+CM, using urn randomization to ensure balance between groups on baseline EA level, coded as "high" if AIS score > 45, or "low"≤ 45. Subjects in both treatments will be scheduled to attend three clinic visits per week (MWF) during the 4-week period. **Two** of these weekly visits will include 1-hour therapy sessions (ACT or DC).

Acceptance and Commitment Therapy-Cocaine Use (ACT). The overarching goal of ACT is to decrease experiential avoidance while increasing acceptance and willingness to experience unpleasant thoughts, feelings, and physical symptoms. More specifically, ACT will assist cocaine patients to notice their internal cravings and triggers, abandon their attempts to manage these triggers via active avoidance, suppression or other control-based strategies, and to make commitments to engage in behaviors consistent with their chosen values or goals. ACT encourages clients to experience thoughts and feelings from an observer perspective, and helps them not to believe distressing thoughts and feelings as if they are literally true and in need of action. ACT treatment will be based on the therapy manual developed and tested previously.^{38, 39} The manual covers 10 core topics listed in **Table B.3.2.vi.** Our experienced ACT therapists will be taught to use the manual as a map with flexibility to "go with the client" so long as issues of acceptance, diffusion, values, and committed action are thoroughly covered. Mindfulness exercises, metaphors, and homework sheets will be used to pursue therapeutic goals, more so than didactic instruction. Masters-level therapists with ACT experience from our previous trial ³⁸ will be trained and supervised by [name] (Co-I) and [name] (Consultant).

Drug Counseling (DC). We will use the manual-guided individual DC modeled after the NIDA Collaborative Cocaine Treatment Study ⁴⁰ and used as the active control therapy in our previous studies.^{38, 41, 42} DC approximates clinical practice as it is considered the most common type of evidence-

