Experiential Avoidance: The *Avoidance and Inflexibility Scale (AIS)* is a 13-item self-report measure, on which respondents indicate, using a 5-point Likert-style scale, their level of avoidance and inflexibility with regard to internal experiences. The AIS has been adapted for several substance-using and other populations,^{38, 48} and in our previous study was modified for cocaine users. Higher scores indicate more avoidant and inflexible responses to internal states associated with cocaine use. The internal consistency of the AIS in our past studies was .89. The AIS will be used as the stratification variable for initial randomization. High avoidance will be defined as AIS scores > 45, based on our preliminary data, showing that this cutoff score distinguished CM responders from non-responders with good sensitivity and specificity indices. The *Acceptance and Action Questionnaire for Substance Abuse (AAQ-SA)* is an 18-item self-report measure on which respondents rate their urges on a 7-point Likert-type scale (1 = “never true” to 7 = “always true”). The AAQ is the standard measure of psychological flexibility. The AAQ-SA is the substance abuse focused version of this measure and has demonstrated good internal consistency, factor structure, and construct validity.¹⁰² The *Valuing Questionnaire (VQ)* is a 10-item self-report measure that assesses the effectiveness of ACT interventions using a 6-point Likert-type scale (1 = “Not at all true” to 6 = “Completely true”). The VQ should provide ACT researchers a convenient, reliable, valid measure for evaluating ACT interventions.¹⁰³ The *Five Facet Mindfulness Questionnaire (FFMQ)* is a 39-item self-report consisting of five subscales (observing, describing, acting with awareness, non-judging of inner experience, and non-reactivity to inner experience) that assess a participant’s mindfulness based on a 5-point Likert-type scale (1 = “Never or very rarely true” to 5 = “Very often or always true”). Mindfulness facets have been found to be significantly related to meditation experience, psychological symptoms and well-being.¹⁰⁴ The *PTSD checklist (PCL-5)* is a 20-item self-report checklist of traumatic events, PTSD symptoms and severity rated on a 5-point Likert-type scale (0 = “Not at all” to 4 = “Extremely”) and will be used to assess new or worsening trauma symptoms. The *Distress Tolerance Scale (DTS)* is a 15-item self-report measure on which respondents indicate, on a 5-point Likert-type scale (1 = “strongly agree” to 5 = “strongly disagree”), the extent to which they believe they can experience and withstand distressing emotional states (e.g., “I can’t handle feeling distressed or upset”). The internal consistency of the DTS is $\geq .82$.⁴⁹ A *Cold Pressor Task (CPT)* will be implemented as an index of physical distress tolerance, otherwise conceptualized as EA of physical distress.⁵⁰ This task involves continual application of a cold stimulus, intended to be safe but aversive, to the hand up to the wrist. Consistent with prior work, we will use ice water (1°C; 33°F) and instruct participants to keep hands still while submerged.⁵¹ Pain threshold is defined as the length of time (in sec) until a self-report of pain is made by the participant. Tolerance is defined as the length of time (in sec) until participant reports that the pain or discomfort is no longer tolerable and/or spontaneous termination of the procedure. Endurance is defined as tolerance minus threshold.⁵² It should be noted that, in the absence of gold standard self-report or behavioral measures of experiential avoidance or emotional tolerance, the measures selected have shown the most relevance to the mechanisms of interest in the present study based on past work.

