Hyp. 1.a. The benefit of ACT+CM over DC+CM on initial response (abstinence) rates will be greater in the subgroup of individuals with higher pretreatment EA scores. Adding the interaction term (EA-by treatment) to the logistic regression model will evaluate the moderating effect of EA.

Hyp. 1.b. ACT+CM effects on initial treatment response will be mediated by the primary hypothesized treatment mechanisms, EA and reward sensitivity. In the context of the direct effect of treatment on response, mediational modeling will evaluate the *indirect* effect of treatment on response via EA and reward sensitivity variables, using the product moment method with bootstrapped 95% CI and Bayesian posterior distributions.

Hyp. 2. For initial non-responders, continued ACT+CM treatment with pharmacotherapy (modafinil) augmentation will be most effective in promoting abstinence relative to treatment combinations involving DC and/or placebo. Logistic regression will evaluate cocaine abstinence at the end of second treatment in a set of contrasts: (1) modafinil versus placebo within each initial treatment; (2) the sequence of ACT+CM with modafinil augmentation versus DC+CM with modafinil augmentation.

Hyp. 3. For initial responders, continued ACT+CM will be more effective (higher abstinence rates; < 46% relapse rate) than continued DC+CM. Logistic regression will evaluate cocaine abstinence/relapse at end of second treatment as a function of initial treatment (ACT+CM vs DC+CM).

Power. Power estimates for Hypotheses 1, 2 and 3 will use as the primary outcome (i.e., “response”), two consecutive weeks of cocaine abstinence (BE ≤ 150 ng/mL). Initial treatment response (abstinence) rates are expected to be $\sim 40\%$, based on our previous study¹² and pooled data across cocaine clinical trials⁸⁵; however we predict a difference in response rates, favoring ACT+CM over DC+CM by about 20%, constituting a clinically meaningful treatment effect. Among initial non responders, we expect at least a

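### Aim 1.b words the mediators as changes, and the Hyp. 1.b model names no baseline value; an unadjusted change in EA would weaken the EA-to-response path, by an amount the documents do not fix

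*Combined protocol and SAP*

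**What the plan says.** Under Aims and Hypotheses, Aim 1.b is "To determine if the effects of ACT+CM are mediated by changes in EA and reward sensitivity". The hypothesis sentence that follows drops the word for change and says the effects "will be mediated by the primary hypothesized treatment mechanisms, EA and reward sensitivity". In the Analysis Plan, Hyp. 1.b tests mediation through the EA and reward-sensitivity measures "using the product moment method with bootstrapped 95% CI and Bayesian posterior distributions", alongside the direct effect. It does not state whether a mediator is a follow-up or a change score, and it lists no covariates.

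Baseline EA has two other uses. Phase 1 allocation is done "using urn randomization to ensure balance between groups on baseline EA level", with the AIS split at 45. For Hyp. 1.a the plan states: "Adding the interaction term (EA-by treatment) to the logistic regression model will evaluate the moderating effect of EA". Neither places baseline EA in the Hyp. 1.b equations.

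Baseline EA is described as prognostic. Background Information reports that, in an earlier 99-patient study of high-magnitude CM, non-responders had higher pretreatment EA than responders. The Assessment Schedule says of the AIS cutoff that "this cutoff score distinguished CM responders from non-responders with good sensitivity and specificity indices". No effect size, sensitivity or specificity is given. No comparable result is reported for the delay-discounting or purchase-task measures.

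**The concern.** A change score is usually negatively correlated with its own baseline. Patients who start with high EA tend to show the largest falls, and by the protocol's own account they also tend to respond least. Within an arm this works against the association that the mediation model is meant to find, namely that a fall in EA goes with response.

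Randomisation and urn balancing protect the treatment-to-mediator path. They do not protect the mediator-to-response path, which is an observational comparison within arms. If that path is attenuated, so is the product of the two. The trial could then report that EA does not mediate the effect of ACT+CM when it does, although lowering EA is the stated rationale for adding ACT to CM.

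**Working it through.** **Inputs from the documents.** N = 160 in two arms, and the direction of the baseline EA association. No path value or power is stated for Hyp. 1.b (the Power paragraph covers Hypotheses 1, 2 and 3), so there is no plan figure to reproduce.

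**Assumed.** log odds of response = constant + direct effect × T + b·post + c·pre, where b is the effect of follow-up EA (negative) and c the direct effect of baseline EA. r is the pre-post correlation and k = SD(post)/SD(pre), with SD(pre) = 1.

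**1. Slope on the unadjusted change, divided by b (linear approximation)**

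ratio = [(k² - rk) + (c/b)(rk - 1)] / (k² + 1 - 2rk)

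At k = 1 this is (1 - c/b)/2 for any r: 1.00, 0.75, 0.50, 0.25 and 0.00 at c/b = -1, -0.5, 0, 0.5 and 1. A logistic simulation with n = 400,000 and b = -0.8 gave 1.00, about 0.73, 0.45, 0.20 and 0.00. With k from 0.8 to 1.25 and r from 0.3 to 0.7, the c = 0 ratio runs from 0.15 to 0.85 and the c = b ratio from -0.69 to 0.69.

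**2. What the documented direction implies.** The unadjusted slope of response on baseline EA is b·rk + c. Higher baseline EA going with poorer response, with b < 0, means c/b > -rk. If rk < 1 (ordinary regression to the mean), the ratio falls as c/b rises, so

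ratio < [(k² - rk) + rk(1 - rk)] / (k² + 1 - 2rk) = 1 - (1 - rk)² / (k² + 1 - 2rk)

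This is below 1, so some attenuation follows. At k = 1 the bound is (1 + r)/2, which is 0.75 at r = 0.5. At k = 1.25, r = 0.6 it is 1 - 0.0625/1.0625 = 0.94, so the loss need not be large.

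**3. Simulated trials at N = 160.** ACT lowers EA by 0.5 SD, the direct effect is 0.4 log-odds and r = 0.6. Detection means that 95% Monte Carlo limits for the indirect effect exclude zero. Loss = 1 - (change path / adjusted path).

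| b, c, k | Formula ratio | Path: change v adjusted | Loss | Detection: change v adjusted |
|---|---|---|---|---|
| -0.7, 0, 1 | 0.50 | -0.33 v -0.72 | 54% | 0.39 v 0.88 |
| -0.7, +0.2, 1 | 0.64 | -0.45 v -0.74 | 39% | 0.60 v 0.90 |
| -0.7, +0.35, 1 | 0.75 | -0.53 v -0.73 | 27% | 0.73 v 0.88 |
| -0.7, 0, 1.25 | 0.76 | -0.50 v -0.73 | 32% | 0.72 v 0.86 |
| -0.7, +0.35, 1.25 | 0.88 | -0.62 v -0.73 | 15% | 0.84 v 0.88 |
| -0.5, -0.25, 1 | 0.25 | -0.12 v -0.52 | 77% | 0.08 v 0.63 |
| -0.5, -0.5, 1 | 0.00 | 0.00 v -0.52 | 100% | 0.02 v 0.59 |
| -0.5, +0.5, 1 (pure change) | 1.00 | no loss | 0% | 0.70 v 0.65 |

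Repeat runs agreed within simulation error; the smallest loss was 14% in one, and the pure-change row gave 0.73 v 0.67 in another. In the first row's setting, r = 0.4 and 0.8 gave detection of 0.45 v 0.88 and 0.24 v 0.67.

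**4. Follow-up EA alone.** Slope / b = 1 + (c/b)·r/k. At r = 0.6, k = 1, b = -0.5: c = b gives 1.6 × -0.5 = -0.80, and c = -b gives 0.4 × -0.5 = -0.20. Simulation gave the same values.

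**5. Baseline-adjusted model.** In the n = 400,000 runs the path was -0.79 to -0.80 against a true -0.80 for every combination of r (0.3, 0.5, 0.7) and the five c/b values.

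**The case against.** The strongest reply is that the plan never adopts a raw change score. Change appears only in the aim sentence; the hypothesis and the analysis text name EA and reward sensitivity without it, and baseline is nowhere excluded. Mediation by change is ordinary wording that also fits a baseline-adjusted follow-up score. This stands: a reader might infer a commitment to raw change, but no formula or covariate list says so.

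It is also tempting to say that the path is halved or cancelled because baseline EA predicts response. The documents do not support that. They give none of b, c, r or k. At equal SDs with c = 0 the ratio is one half for any r, including r = 0, when baseline EA would not predict response at all. The prognostic evidence therefore supports the direction of the bias and does not set its size. Cancellation at equal SDs needs a direct baseline effect equal to that of follow-up EA. The evidence offered is an unadjusted association, without effect size, from one earlier study.

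Nor does the argument extend to reward sensitivity, where no prognostic finding is reported. And Hyp. 1.b is a mechanism question with no power claim, while the Go criterion concerns the probability of treatment benefit.

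What does not stand is that only detail is missing. Without baseline, both natural readings of the mediator (change, or follow-up value alone) give a biased path except in special cases. For change, the exception at equal SDs is c = -b. The unadjusted baseline slope is then b(r - 1), which is positive for b < 0 and r < 1, so higher baseline EA would go with better response. The protocol reports the opposite.

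**Conclusion.** The point holds in conditional form. The aim speaks of change, no baseline mediator value is named in either Hyp. 1.b equation, and baseline EA is documented as prognostic in the adverse direction. If unadjusted change in EA is used, some attenuation of the EA-to-response path follows, given that follow-up EA regresses towards the mean (rk < 1).

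The loss is about half if response depends on follow-up EA only with equal SDs, and about 14% to 40% in the settings tried with an opposing direct baseline effect or a larger follow-up SD. It is complete, at equal SDs, only if the two direct effects are equal; a smaller follow-up SD makes the loss worse. All sizes rest on assumed effects, correlations and SDs.

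For reward sensitivity the change is precautionary. The Hyp. 1 comparison, the Phase 2 contrasts and the Go rule are unaffected. The correction should be made because the biased result would bear on the trial's stated mechanism and the remedy is nearly free.

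**What to change.** In Hyp. 1.b, define each mediator as its follow-up value at a named visit, and include its baseline value as a covariate in both the mediator and the response equation. Use continuous baseline AIS for EA rather than the split at 45, and the baseline delay-discounting and purchase-task indices for reward sensitivity.

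The aim's wording can stay. Since b·post + c·pre = b·(post - pre) + (b + c)·pre, a change score with baseline in the model has the same mediator coefficient as the follow-up value with baseline.

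The cost is SAP wording; for EA, the baseline AIS is already collected for allocation. The downside is slightly lower power if response depends purely on change: detection of about 0.67 instead of 0.73 in simulation (0.65 instead of 0.70 in another run). Baseline adjustment does not settle whether the mediator changed before abstinence began, which is a separate question.

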Developing adaptive interventions for cocaine cessation and relapse prevention; Using event-related potentials to predict treatment outcomes in cocaine use disorder (“Adaptive trial”)

NCT02896712

Version Date: 06/15/2020

Protocol Title:	Developing adaptive interventions for cocaine cessation and relapse prevention; Using event-related potentials to predict treatment outcomes in cocaine use disorder ("Adaptive trial")
Principal Investigator:	[name]
Co-Investigators:	[name], [name], [name], [name], [name], [name], [name], [name]
Study Coordinator:	[name]
Population:	N = 160 adults (18-60 years old) with cocaine use disorder recruited from the Houston metropolitan area
Number of Sites:	Single site
Study Duration:	Four years
Study Duration per subject:	14 weeks, with 3 visits per week for a total of 42 study visits

Project Summary

Drug addiction is a chronic, devastating, but *treatable* disorder, for which there exists a growing armamentarium of evidence-based interventions, including pharmacotherapies and psychotherapies. A core principle of drug addiction treatment, however, states that *no single treatment is appropriate for everyone*; rather, treatments need to be adjusted based on patient characteristics and response in order to be maximally effective. Ideally, clinicians would identify a sequence of interventions that works best across different stages of addiction treatment, from abstinence initiation to relapse prevention. Adaptive treatment interventions have been used successfully to inform this sequential clinical decision-making process. For cocaine use disorders (CUD), the most potent intervention currently available for initiating abstinence is behavior therapy using contingency management (CM) procedures. Intensive CM has been shown to produce initial cocaine abstinence rates of 40%, unmatched by all other forms of behavioral or pharmacological treatment, making it a prototypical first-line therapy for CUD. Importantly, achievement of initial abstinence predicts future abstinence. For the clinician, these research findings translate into a straightforward question: *Can we drive CM response rates even higher with targeted adjunctive interventions?*

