based treatment in the community for patients actively using cocaine. DC educates patients about important concepts in addiction recovery based on the underlying philosophy that physical, emotional, spiritual, and interpersonal needs must all be addressed to support recovery. Accordingly, the DC manual covers the core topics listed in **Table B.3.2.vi**. Masters-level therapists with DC experience from our previous trials^{41, 42} will be trained and supervised by [name] (Co-I).

Contingency Management (CM). We will use the same high-magnitude CM schedule shown previously to be feasible and effective in facilitating initial cocaine abstinence.¹² Subjects will earn vouchers for cocaine-negative urine samples collected at scheduled clinic visits (MWF) each week. Under an escalating reinforcement schedule, voucher values will begin at \$15 and increase by \$10 for each consecutive negative urine. Provision of a cocaine-positive urine or failure to provide a scheduled sample will result in no vouchers earned and will reset the schedule to the initial value (\$15). Bonus vouchers (\$10) will be given for completing all study-related tasks in a given week. Subjects will redeem their earned vouchers for cash loaded to the ClinCard, a reloadable debit card.

Initial response and re-randomization. Following Phase 1 treatment, the primary outcome of response/non-response will be determined. Subjects who submit 6 consecutive (2 weeks) cocaine negative urine samples by week 4 will be classified as responders. Those who fail to meet response criteria will be classified as non-responders.

During second (Phase 2) treatment:

- Responders will continue to receive their assigned initial treatment, as described below.
- Non-responders in each initial treatment arm will be re-randomized to a second treatment consisting of pharmacotherapy augmentation with either modafinil or placebo.

All subjects will attend three clinic visits per week (MWF) during the 8 week second treatment period.

Table B.3.2.vi. 10 Core Topics for ACT and DC

Second (Phase 2) treatments	ACT	DC
Continued ACT or DC. Twice weekly 1-hour ACT and DC sessions will continue during the 8 weeks of second treatment, covering the core topics shown in Table B.3.2.vi.	Preparing to begin	Planning my recovery
	Values	Stages of recovery
	Making contact with the cost of using	People, places, things
	Creative hopelessness	Self-help groups & support systems
	Control v Willingness	Establishing a support system

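### The modafinil/placebo re-randomisation and the Hyp. 2 model use no Phase 1 urine information beyond the yes/no response rule, which costs a modest amount of precision in small cells

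*Combined protocol and SAP*

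**What the plan says.** All references are to the combined protocol and SAP.

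- **Phase 1 treatments:** participants are "scheduled to attend three clinic visits per week (MWF) during the 4-week period", which gives 3 × 4 = 12 scheduled urines.
- **Initial response and re-randomization:** "Subjects who submit 6 consecutive (2 weeks) cocaine negative urine samples by week 4 will be classified as responders". For everyone else: "Non-responders in each initial treatment arm will be re-randomized to a second treatment consisting of pharmacotherapy augmentation with either modafinil or placebo". No stratification or balancing variable is given for this second step.
- **Assessment Schedule, Experiential Avoidance:** "The AIS will be used as the stratification variable for initial randomization". This is the only balancing variable named, and it is tied to the first randomisation. The legend under Overview of Study Design separates the two kinds of step: "SR=stratified randomization; R=randomization".
- **Hypothesis testing, Hyp. 2:** "Logistic regression will evaluate cocaine abstinence at the end of second treatment in a set of contrasts". The contrasts are modafinil versus placebo within each initial arm, and ACT+CM with modafinil versus DC+CM with modafinil. No covariate is named. Under Analytic strategy the re-randomised groups are coded with 0/1 indicators. Inverse probability weighting is mentioned but not linked to Phase 1 urines.
- **Prognosis:** the Project Summary says "Importantly, achievement of initial abstinence predicts future abstinence", and Background Information calls early abstinence a robust predictor. Background also says little is known about what predicts response to contingency management, "with the exception of intake urine status considered a marker of disorder severity".

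**The concern.** The non-responder group mixes patients who never gave a negative urine with patients who narrowly missed six in a row. Their Phase 1 record is complete just before the second randomisation and comes from the same assay as the Hyp. 2 outcome. If that record predicts Phase 2 abstinence, a small cell that happens to draw more near-responders will look better or worse for reasons unrelated to modafinil. Under Power, the plan treats a posterior probability of benefit above 0.80 as enough for a Go decision. At that threshold a shift of a few points in the estimate can matter. Balancing and adjustment would use data the trial already collects.

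**Working it through.** **1. The plan's own figure.** Table B.3.2.x gives power 0.81 for contrast 5 vs 6 (effect 0.17) and for 7 vs 8 (effect 0.13), at posterior probability 0.80. I take 5 vs 6 as the ACT arm and 7 vs 8 as the DC arm, because the figure is not shown. With vague priors the rule is close to a one-sided test at 0.20, so

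power = Φ((δ − 0.8416·s0)/s1), with s0 = √(2p̄(1−p̄)/n) and s1 = √((p0(1−p0)+p1(1−p1))/n).

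Example: p0 = 0.02, δ = 0.17, n = 16 gives s0 = 0.1084, s1 = 0.1041, and (0.17 − 0.0912)/0.1041 = 0.757, so power is 0.78.

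| Placebo abstinence (assumed) | 5 vs 6, n = 16–20 | 7 vs 8, n = 24–28 |
|---|---|---|
| 2% | 0.78–0.83 | 0.79–0.82 |
| 5% | 0.72–0.78 | 0.72–0.76 |
| 20% | 0.59–0.64 | 0.57–0.60 |

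The placebo rate is in the missing figure, so 0.81 can be neither confirmed nor called wrong.

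**2. Cell sizes.** Inputs are N = 160, response of about 40% and a 20-point difference (Power), with 1:1 allocation assumed at both stages. Cell size is 80 × (1 − response)/2.
- Response 60%/40% (ACT/DC): 80 × 0.40/2 = 16 and 80 × 0.60/2 = 24.
- Response 50%/30%: 80 × 0.50/2 = 20 and 80 × 0.70/2 = 28.

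**3. Spread within non-responders.** The longest record without six in a row is five negatives, a break, five negatives, a break: 10 of 12. Enumerating all 2^12 = 4,096 sequences confirms a range of 0 to 10. A responder can have as few as 6.

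**4. Chance imbalance (hypergeometric, equal cells).** Near-responders are assumed to be 25–50% of non-responders. The chance that their share differs by 20 points or more between modafinil and placebo is:

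| n per cell | 25% near-responders | 50% near-responders |
|---|---|---|
| 16 | 0.22 | 0.29 |
| 20 | 0.27 | 0.34 |
| 24 | 0.09 | 0.15 |
| 28 | 0.12 | 0.18 |

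The order is not smooth because only certain differences are possible at each n. The SD of the difference falls steadily, from 0.156–0.180 at n = 16 to 0.117–0.135 at n = 28.

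**5. Effect on the estimate.** Shift = imbalance × prognostic gap. For a 20-point imbalance: 0.20 × 10 = 2 points, 0.20 × 25 = 5 points, 0.20 × 40 = 8 points. The planned effects are 13 and 17 points. The unadjusted SD of the difference is about 14–17 points at n = 16 and 10–12 points at n = 28.

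**6. Gain from balancing and adjusting.** This is a 40,000-run simulation with a two-level urine stratum: simple re-randomisation with an unadjusted analysis, against stratified re-randomisation with a post-stratified analysis. Power ≈ Φ(δ/SD − 0.8416).

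| Assumed placebo rates, others vs near-responders | Variance cut | Power gain | Example |
|---|---|---|---|
| 2% vs 40% (33% near) or 5% vs 45% (50% near) | 18–22% | 4–6 points | n = 16, δ = 0.17: SD 0.147 to 0.132, power 0.62 to 0.67 |
| 5% vs 30% (33% near) | 7–11% | 1–3 points | n = 16, δ = 0.17: SD 0.143 to 0.137, power 0.64 to 0.66 |
| 10% vs 20% (33% near) | about 0–3% | at most about 1 point | n = 28, δ = 0.13: SD 0.105 to 0.104, power 0.655 to 0.658 |

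A separate patient-level model (between-patient logit SD 2–4, Phase 1 to Phase 2 correlation 0.5–0.9, 40% response, all assumed) gives a gap of only 12–18 points for a split at 0–3 versus 4 or more negatives. Linear adjustment done separately in each contrast, at 16–24 per cell, then changes the variance by about −1% to +5%.

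**7. A limit from step 1.** The stated 0.81 is reachable only if placebo abstinence is about 2–3%. At 2% overall with 33% near-responders, the near-responders' placebo rate cannot exceed 0.02/0.33 = 6%. The placebo gap is then below even the smallest one in step 6.

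**The case against.** Simple re-randomisation with an unadjusted contrast is a legitimate choice for a secondary aim in a Stage II Go/No-Go trial, and the unadjusted posterior already carries chance imbalance in its width. That stands. A reader might infer that the modafinil-placebo comparison is biased. It is not, since treatment is randomised within each initial arm.

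A reader might also infer that the Phase 1 urines are ignored altogether. They decide who is a responder and who is re-randomised. Only the variation among non-responders goes unused.

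Nor do the documents show that partial abstinence among non-responders is prognostic. The feasibility result in Background compares responders with non-responders, and the intake-urine remark concerns response to contingency management. Prognosis within non-responders is a reasonable extension, but an assumption.

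Finally, adjustment is not free. If placebo abstinence is 8–20% (assumed), a cell of 16 has about 16 × 0.08 = 1.3 to 16 × 0.20 = 3.2 placebo events. At 8% the chance of none is 0.92^16 = 0.26. A coefficient prior of N(0, 1×10^6) gives no protection against separation there. The count also mixes attendance with use, because the primary analysis imputes missing observations as positive.

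None of this removes the gap in the plan. It limits the likely benefit and shapes the remedy. The contrast between ACT+CM with modafinil and DC+CM with modafinil raises a different issue, selection on initial response, which a covariate would not fully remove. This point does not rest on it.

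**Conclusion.** The point holds as a missed, low-cost precision measure. No balancing factor is named for the re-randomisation and no covariate for Hyp. 2, so non-responders with 0 to 10 negatives of 12 are handled alike. The cost is some loss of precision and exposure to chance imbalance in cells of about 16–28. The likely power gain is about 0–6 points across assumed gaps of 10 to 40 points, and near zero at the low end or if placebo abstinence is as low as the stated power seems to need. These sizes rest on 1:1 allocation at both stages and on assumed urine distributions and prognostic gaps. The planned cell sizes and rates are in a figure that is not shown. The documents support neither a claim of bias nor a claim that the stated power is wrong.

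**What to change.** - **Re-randomisation:** within each initial arm, balance modafinil/placebo on a Phase 1 urine summary, for example the number of negatives in two levels, with the urn method already used at the first randomisation. The cut should be fixed in advance; the documents do not point to one.
- **Hyp. 2 model:** prespecify the count as a single covariate with a common slope across the Hyp. 2 cells. Put a weakly informative prior on its coefficient instead of N(0, 1×10^6), to guard against separation.
- **Reporting:** give the covariate-standardised risk difference beside the unadjusted one, and state how missed visits enter the count.

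The cost is one more urn factor, one more parameter in sparse cells, and a covariate that partly measures attendance. No new data are needed. If re-randomisation is already complete, only the covariate applies, and it should be specified before unblinding.
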